### **6: STUDY POPULATION**

20 participants will be recruited from each arm of the study, resulting in a total of 40 valid subjects. Although we will initially recruit 50 subjects, we expect an attrition rate of 20%.

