# 8.4 Methodology

The following tasks will be conducted on the recruitment day (Day 0) for all subjects, and will be recorded in each subject's respective source documents and case report forms (CRFs):

- 1. Assessment of eligibility against inclusion and exclusion criteria
- 2. An explanation of study procedures.
- 3. Provision and obtainment of written informed consent.
- 4. Obtainment of demographic information and medical history.
- 5. Booking of Day 1 and Day 2 (based on convenience).

The main study will be conducted over 2 consecutive days for each subject.

Participants will be asked to complete each of the following - 30 minutes prior to their appointment on Day 1; the Oswestry Disability Index (ODI), a Numeric Rating Scale for Pain (NRS Pain), the Roland Morris Disability Questionnaire, and a Low Back Pain Classifier.

Both subject groups will then have a "start interview" on their allocated baseline assessment day (Day 1). This will include fitting of the ViMove movement and EMG sensors, as well as a ViMove live "pain on movement" assessment. This session will take approximately 20-30 minutes. Whilst wearing the ViMove sensors, subjects will then leave the clinic and conduct normal daily activities for a predetermined monitoring period. No ThermaCare HeatWraps are worn on Day 1. This allows a baseline assessment and allows any placebo effects from the sensors to be discounted. At the end of the monitoring session, subjects will return to the clinic to have an "end-of-day" interview. Participants will complete a Patient Global Impression of Change scale (PGIC), a repeat NRS, and will have another live ViMove assessment. Movement sensors will then be removed, and the subject will be reimbursed for that day.

The intervention day (Day 2) will have the same procedure as Day 1 (baseline), with the only difference being the additional application of ThermaCare HeatWraps during the "start interview". ThermaCare will only be applied after the live assessment, so will not be worn at the same time as the EMG sensors. Subjects will continue to wear the HeatWrap and ViMove sensors during the 8-hour daily activity monitoring period, with the wrap and sensors being removed during the end-of-day interview, prior to the end-of-day live assessment. The subject will then be reimbursed for Day 2. A schedule of events can be seen in Table 1, and a summary of the procedure can be seen in Figure 1.

Table 1. Schedule of Events

[figure not shown]

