Tuble 1: Senedale of Events	Visit 1*	Visit 2*	Visit 3	Visit 4	Visit 5
		Baseline	Baseline	Intervention	
	(Day 0) Enrol-	Baseline Start	End of	Start	Intervention End of Day
		Interview		Interview	Interview
	ment		Day	interview	interview
		(within 3 weeks of	Interview		
		Visit 1)			
Eligibility	х				
Informed consent	х				
Demographics & Medical History	Х				
Enrolment and scheduling	Х				
Questionnaires		x		x	х
ViMove application		х		х	
ViMove in clinic assessment		х	Х	х	Х
ViMove monitoring assessment		х		х	
ViMove removal			Х		Х
ThermaCare application				х	
ThermaCare removal					Х
Adverse Events		х	Х	х	Х
Changes in medications		х		х	
Study Termination					х

\*Baseline may occur on the same day as Visit 1 (i.e. enrolment).

Subjects who withdraw from the study after providing informed consent are referred to as "dropouts" or premature withdrawals. The drop-out rate will be summarized. If the patient has provided a whole set of Day 1 data, this will be included in the study.

We expect 6-months will be required from first participant enrolment to the last participant visit. A further 3-months will be required for analysis and write-up.

Figure 1. Summarized Procedure

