### 11.2 Statistical Methods

An initial descriptive analysis will be completed on the baseline measures of movement to determine mean scores, ranges and standard deviations of each sample group. This analysis will be repeated at later time points. Wilcoxon Signed Ranked Tests will be completed to determine if participant movement significantly changes following an intervention: One each for Baseline and Intervention. A repeated measures ANOVA will then be completed on all post trial data for the 2 separate groups to determine movement changes in the post-trial period.

Bivariate correlational analyses through the Pearson product-moment coefficient, will be undertaken to determine if there is a relationship between movement and "pain on movement" using data collected at each time point. This potential relationship will be mapped to assess any temporal influences.

Similarly, correlational analyses will be conducted to determine if there is a relationship between daily activity and ODI scores, using data collected at each of the four total time points. This potential relationship will also be mapped over time to determine if there are any temporal effects following initial treatment.

All findings with a p-value < 0.05 will be deemed significant.

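### No common analysis set is defined for the no-heat day and the heat day, so a Day 2 versus Day 1 comparison can be biased, in either direction, if dropout depends on the Day 1 change

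*Combined protocol and SAP*

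**What the plan says.** Every subject has a no-heat day followed by a heat day. Section 8.4 states that "No ThermaCare HeatWraps are worn on Day 1" and gives the purpose of that day as a baseline and a way to discount placebo effects of the sensors. Each day has a live assessment at its start and end, so a subject with both days has four.

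For subjects who leave early, the text after Table 1 in section 8.4 says "The drop-out rate will be summarized", and then: "If the patient has provided a whole set of Day 1 data, this will be included in the study". It does not say which analysis the retained data enter.

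Section 11.2 plans Wilcoxon signed-rank tests of change in movement, "One each for Baseline and Intervention". It then adds: "A repeated measures ANOVA will then be completed on all post trial data for the 2 separate groups". It names no common subject set, no method for missing Day 2 data and no direct Day 2 versus Day 1 Wilcoxon test. The significance rule is "All findings with a p-value < 0.05 will be deemed significant".

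On numbers, section 6 says "20 participants will be recruited from each arm of the study, resulting in a total of 40 valid subjects" without defining a valid subject. Sections 6 and 11.1 expect 20% attrition from 50 recruited.

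**The concern.** The study has no randomized control (section 8.2), so Day 1 is the only no-heat reference. Any attribution of a Day 2 change to the wrap rests on reading Day 2 against Day 1, whether formally or by eye from the two p-values. Under the text as written, the Day 1 result may come from everyone who finished Day 1 and the Day 2 result only from those who returned. If those who return differ in how they change within a day, part of the contrast reflects who came back.

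The N is also unclear. A Day 1-only subject counts as included in the study yet has no reading under heat. The pilot is meant to guide an RCT (sections 8.2 and 11.1), so the effect estimate and the retention count are among its main products.

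**Working it through.** **Plan's own figure.** Recruitment needed = 40 / (1 − 0.20) = 50, which matches sections 6 and 11.1. Per group, assuming an equal split, 20 / (1 − 0.20) = 25. No effect size, SD or power is stated, so there is nothing else to reproduce.

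**Largest mismatch.** If all losses follow a complete Day 1, the tests have 25 and 20 subjects per group, so 5 of 25 (20%) are in the no-heat test only. Earlier losses shrink this.

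**Bias algebra.** Let d1 and d2 be a subject's within-day changes on Days 1 and 2, scaled to SD 1 and coded so that positive is better. Let rho be their correlation, with no heat or time effect. Let m be the expected mean of d1 among completers, when loss depends on d1.

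- All Day 1 subjects: mean d1 = 0.
- Completers: mean d1 = m and mean d2 = rho × m.
- Day 2 completers minus all of Day 1: bias = rho × m.
- Day 2 minus Day 1 in completers only: bias = rho × m − m = (rho − 1) × m.

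**Numbers put in.** Assumptions, none of them in the documents: 25 start, 5 are lost, normal changes, and dropouts are ranked on −k × d1 plus noise. At rho = 0.5:

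| Selection strength k | All Day 1 subjects kept (SD) | Implied m (SD) | Completers only (SD) |
|---|---|---|---|
| 0.5 | +0.077 | 0.077 / 0.5 = 0.15 | −0.076 |
| 1.0 | +0.123 | 0.123 / 0.5 = 0.25 | −0.117 |
| 1.5 | +0.142 | 0.142 / 0.5 = 0.28 | −0.138 |

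The two columns mirror each other because rho and 1 − rho are equal at 0.5.

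**Dependence on rho and on who leaves** (Day 2 completers minus all of Day 1, in SD):

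| Who leaves | rho 0 | rho 0.3 | rho 0.5 | rho 0.8 |
|---|---|---|---|---|
| Random 5 | about 0 | about 0 | about 0 | about 0 |
| 5 worst Day 1 changers | 0.01 | 0.10 | 0.17 | 0.27 |
| 5 best Day 1 changers | 0 | −0.11 | −0.17 | −0.27 |

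**Effect on the planned tests.** Under the extreme case (5 worst lost, two-sided 0.05 assumed), Day 2 is significant in favour and Day 1 is not in 10.9% of null groups at rho 0.5 and 22.6% at rho 0.8. With the same 20 subjects in both tests the figures are 3.9% and 5.2%. With random loss the figure is about 2%.

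**Likelihood estimate from all Day 1 data plus completers' Day 2 data.** Its bias was within 0.004 SD of zero in every setting run in which loss depended on the observed Day 1 change.

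**The case against.** Several counter-arguments stand in whole or in part.

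- **Retained is not the same as tested.** Section 8.4 says only that the data are included in the study. They may be meant for the descriptive baseline summary in section 11.2. This is fair, but nothing excludes them from the Day 1 Wilcoxon test, and that silence is the defect.
- **Keeping the data is not the error.** Retention leaves the Day 2 test unchanged, and under this model the all-subject Day 1 mean is unbiased. The distortion comes from who is left on Day 2. This stands, and the fix should not discard Day 1-only data.
- **Completers-only is no cure.** Its bias is (rho − 1) × m. At rho 0.5 that is about −0.07 to −0.14 SD, and at rho 0 it is −0.15 to −0.28 SD while the all-data contrast has none. It has the smaller bias only when rho exceeds 0.5. This stands.
- **The size is modest.** Days 1 and 2 are consecutive. The start of Day 1 may be up to 3 weeks after enrolment, and dropouts are counted from consent, so some losses will come earlier. A bias of 0.08 to 0.14 SD compares with a sampling SD of about 0.22 for the same contrast. This also stands.

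Two stronger readings are tempting. A reader might infer that subjects who worsen on Day 1 stay away, so that the bias favours heat. The documents do not say so. The withdrawal reasons in section 7.3 include sensor compliance, co-operation, serious events and pregnancy, and a subject who feels better could equally skip Day 2. Because each test is within-day and paired, losing subjects with worse levels but the same change does no harm.

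A reader might also reason that five dropouts who are 1 SD worse on Day 1 create a gap of 5/25 × 1 = 0.20 SD even if their Day 2 change is unrelated to Day 1. If it is unrelated and there is no heat or time effect, completers' expected Day 2 change equals the whole group's, and the expected gap is 0. Simulation of that case gave 0.001 SD.

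**Conclusion.** The point holds as a gap in the plan with a conditional bias. Sections 8.4 and 11.2 allow the no-heat and heat results to rest on different subjects, up to 25 against 20 per group, and give no rule for the comparison between days. Bias needs two things together: loss that depends on the within-day Day 1 change, and correlation of that change with the Day 2 change. Under the assumed selection and a correlation of 0.5 it is about 0.08 to 0.14 SD. It vanishes at correlation 0 or with random loss, and it reverses, masking a real effect, if the best changers leave. Correlation, SD scale and dropout mechanism are all assumptions. The documents do not support a claim that heat is favoured.

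**What to change.** In sections 8.4 and 11.2:

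1. Estimate Day 2 versus Day 1 (the difference between the two within-day changes) with a mixed model fitted, within each group, to all available readings from the four live assessments. Include Day 1-only subjects. This replaces the repeated measures ANOVA, which ordinarily drops subjects without Day 2 data. The covariance of the four readings should be unstructured. A subject random intercept alone, with variance t, gives a covariance between the two daily changes of t − t − t + t = 0, so it cannot use the correlation that corrects the bias.
2. Beside it, show the paired result in subjects with both days complete, as a sensitivity analysis. State that it is itself biased when loss depends on the Day 1 change.
3. Say which subjects enter each Wilcoxon test.
4. Tabulate Visit 2 and Visit 3 values of dropouts against completers.
5. Define a valid subject, and report N for enrolled, Day 1 complete and both days complete.

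The cost is a few sentences and slightly more analysis work, with no new data. The model assumes that loss depends only on observed readings. The data cannot verify this; the table in item 4 only shows whether loss is related to the observed Day 1 values.

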### 8.5 Measurement Tools Used

# 8.5.1 ViMove Live – Range of Movement and Surface Muscle Activity

ViMove is a validated and reliable tool used for measuring movement and muscle activity of the low back. The ViMove devices will be fitted during the "start interview". This requires the attachment of the sensors to skin over the lumbar region with adhesive pads using the standardized protocol. ViMove will be used to provide the primary outcome measures relating to movement data, surface muscle activity and recording pain on movement.

# 8.5.2 ViMove – Pain on movement

Pain on movement compares subjective responses of pain, with objective movement data from ViMove sensors. Assessment requires subjects to move within a maximum tolerable range. A numeric pain rating scale (see below) will be used during each movement, to obtain a value for the level of pain that each subject experiences. Consistent and standardized instructions are used, with the pain scores being recorded in the ViMove system. If no pain on movement is reported, a score of 0 will be documented.

(No Pain) 0 1 2 3 4 5 6 7 8 9 10 (Worst Pain)

# 8.5.3 ViMove – Monitoring (Out-of-clinic Assessment)

The monitoring period, in which subjects wear the ViMove devices during normal daily activity, aims to obtain or assess:

- 1. Total time spent in a dynamic vs. static state.
- 2. Sitting data; number and duration of sitting and walking events.
- 3. Timed walking test.
- 4. Postures and movement data throughout the day.

### 8.5.4 Questionnaires

The following questionnaires will be completed by subjects on a tablet onsite at their respective timepoints.

### Oswestry Disability Index (ODI)

The ODI is a validated self-report questionnaire which quantifies the extent to which a person's functional status is restricted by low back pain, and assesses the associated detriment [23]. It measures disability in the context of pain, rather than considering pain as the impairment. Ten 6-point scales assess the intensity (1) and effect (2) of pain on: personal care, lifting, walking, standing, sleep quality, sexual function, social life, and the ability to travel.

### **Numeric Rating Scale for Pain (NRSP)**

The NRSP is a measure of pain intensity. It consists of a horizontal line anchored by 11 descriptions of pain (no pain vs. worst possible pain). Subjects are asked to circle a value along the line. The scale can be seen below:

(No Pain) 0 1 2 3 4 5 6 7 8 9 10 (Worst Pain)

#### **Roland Morris Disability Questionnaire**

The Roland-Morris Questionnaire (RMDQ) is a self-administered disability measure in which greater levels of disability are reflected by higher numbers on a 24-point scale. The RMQ has been shown to yield reliable measurements, which are valid for inferring the level of disability, and to be sensitive to change over time for groups of patients with LBP.

### Patient's Global Impression of Change Scale (PGIC)

The PGIC assesses a subjects perceived efficacy of a treatment [30]. In the context of this study, it will assess the subject's beliefs around any changes in their low back pain following the use of ViMove only (Baseline [Day 1]), and following the wearing of ViMove + ThermaCare (Intervention [Day 2]) during the respective periods of daily activity/monitoring. This assessment will utilize a 7-point scale as follows:

(1) Very much improved
 (2) Much improved
 (3) Minimally improved
 (5) Minimally worse
 (6) Much worse
 (7) Very much worse

(4) No change

#### Low Back Pain Classifier (LBPC)

The Low Back Pain Classifier (LBPC) is a questionnaire which is available as part of the ViMove software. It can be completed electronically by patients or clinicians. The results are delivered as part of a Low Back Live Assessment Report.

The LBPC was originally developed by [name] and extended/modified by [name]. It was developed to assist clinicians gain a better understanding of the type of movement dysfunction affecting their patients. The questions direct clinicians towards lumbar flexion or extension biased aggravating activities. Questions 1-3 are about flexion aggravating activities and questions 4-6 relate to extension easing activities. Questions 7-9 are about extension aggravating activities whilst the final 3 questions (10-12) are about flexion easing activities. There are now additional questions quantifying walking verses sitting aggravation. These questions serve two purposes: (i) measure walking and sitting with much greater precision than a RMDQ or ODI and (ii) to flag if an extension activity (walking) is better or worse than a flexion (maybe flexion but could be extension or loading problem in an upright sitting posture) activity.

The questionnaire has not been formally validated.

### 9: ANTICIPATED BENEFITS AND RISKS

#### 9.1 Potential Benefits

We cannot guarantee that there will be any benefits from this research. However, possible benefits may include:

#### 1. Personal benefit:

The ViMove in-clinic and monitoring (out-of-clinic) assessment data will be provided to the treating clinician after the baseline and follow-up sessions. Practitioners will receive a report detailing the participant's movements during the assessment periods, and highlighting any abnormal movement patterns. The clinician may use this information to help educate the participant on healthier movement patterns and postures.

ThermaCare HeatWraps may be beneficial due to it being a heat therapy, and the normally associated effects of such therapies.

2. Assisting in the understanding of assessment data:

This study will add to our knowledge of movement and activity in people with low back pain, and specifically how different factors related to back pain are influenced by each other.

3. This study will further our understanding of the roles of both of self-reported functional questionnaires, ViMove data, and ThermaCare in the management and prevention of Low Back Pain.

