However, these studies are limited in their assessment of pain and disability. Pain was often measured using Likert-scale questionnaires, as pain is an inherently subjective experience despite being physiologically determined [19]. Disability was assessed using more comprehensive questionnaires, but was not compared with objective measures [20]. This is despite objective measures of movement being correlated with disability scores [21]. A Cochrane review assessing the efficacy of heat therapies such as ThermaCare, indicated that there is only moderate support from current research, as effects

are transient and relatively small [22]. However, these reviewed studies may be limited due to their qualitative and subjective measurement of pain and disability [23]. A systematic review and meta-analysis further indicated that current heat therapy research is of "very-poor-quality" [24]. As such, validated, objective and quantitative data into muscle activity and movement is required, to provide insight into subjectively reported changes in pain and disability.

Objective assessment of the association between pain and movement, and capturing a detailed view of the person's movement, postures and activity levels is now possible due to the development of portable biofeedback sensors such as ViMove (dorsaVi Ltd). ViMove is wearable sensor technology, designed to precisely measure range of movement and static postures [25-27]. The device also measures low back muscle activity in real time through additional electromyography sensors. ViMove assessment of low back range of movement and posture has been shown to be highly correlated with 3D kinematic measurement [26]. Normative low back range of movement values have also been determined and are available for the adult population (normative data has FDA clearance, available upon request). The device also demonstrates high intra- and inter-rater reliability as a low back measurement tool [27]. Objective information and feedback is provided to the practitioner as a report evaluating a patient's movement and function/activity pre- and post- low back pain intervention. The wearable and portable nature of the device allows monitoring in non-clinical environments for up to 24 hours (i.e. during normal daily activities). ViMove devices have TGA approval and FDA 510K clearance for use in Australia and the USA respectively.

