#### 8.2 Randomization

This study has been designed as an initial feasibility study providing insights that would guide an RCT. As such, this is a non-randomized partially blinded study, as the investigator and participants will be blinded to ViMove results, but not the test condition. Groups will not be randomized, and will be based on recruitment.

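### Could a ViMove report released after Day 1 reach the participant before Day 2 and undo the blinding in section 8.2?

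*Combined protocol and SAP*

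**What the plan says.** Section 9.1 (Personal benefit) states that ViMove in-clinic and monitoring "assessment data will be provided to the treating clinician after the baseline and follow-up sessions". It continues: "Practitioners will receive a report detailing the participant's movements during the assessment periods". On use, it says: "The clinician may use this information to help educate the participant on healthier movement patterns and postures".

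Section 8.2 describes a non-randomised, partially blinded study in which "the investigator and participants will be blinded to ViMove results, but not the test condition". It does not mention the treating clinician or say when the blind ends.

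Section 8.4 fixes the timing of the two study days: "The main study will be conducted over 2 consecutive days for each subject". Day 1 is worn without the wrap, and its purpose is given as follows: "This allows a baseline assessment and allows any placebo effects from the sensors to be discounted". Day 2 repeats the Day 1 procedure, with the wrap as the sole difference. The wrap goes on only after the Visit 4 live assessment.

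Two other places mention reports. Section 2 says in general terms that the device gives feedback to practitioners "as a report evaluating a patient's movement and function/activity pre- and post- low back pain intervention". Section 8.5.4, on the Low Back Pain Classifier, says: "The results are delivered as part of a Low Back Live Assessment Report".

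**The concern.** Read quickly, 9.1 and 8.2 seem to conflict. One blinds participants to ViMove output. The other sends that output to a clinician who may discuss it with them, and the time phrase can be taken to mean after each session. Follow-up session is not a visit name in 8.4 or Table 1, so the terms do not settle the matter. The classifier text suggests that a single live assessment can generate a report, and Day 1 has two live assessments (Visits 2 and 3).

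If a Day 1 report were released that evening and the clinician coached the participant before Visit 4, two things would go wrong. The participant would no longer be blind to the results. Day 2 would also differ from Day 1 by coaching as well as by the wrap. With no concurrent control, the two could not be separated, and Day 1 would lose the control role that 8.4 gives it.

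**Working it through.** The plan gives no figure on this point. Its one reproducible design figure, 40/(1 - 0.20) = 50 recruited, checks out but does not bear on the question. The check is therefore a comparison of sections, a count of endpoints and a short piece of algebra.

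**1. Which reading of 9.1 fits the rest of the plan?**

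| Source | After each session | After both sessions |
|---|---|---|
| 8.2, blinding of participants | Conflicts if the report is passed on before Visit 4 | Consistent through Visit 5 |
| 8.4, wrap as the sole difference between days | Conflicts if coaching occurs overnight | Consistent |
| 8.4 and Table 1, steps between Visits 3 and 4 | No report, feedback or contact listed | None needed |
| 9.1, a report on the assessment periods (plural) | Possible | Natural |
| Section 2, report covering before and after an intervention | Possible | Natural |
| 8.5.4, Low Back Live Assessment Report | Possible; no timing or recipient given | Possible |

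Nothing visible rules out release after each session. Sections 8.2 and 8.4 are the operative sections, and only release after both fits them while allowing the education that 9.1 describes. Section 9.1 lists possible benefits and is not a procedures section.

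**2. Which endpoints would be exposed if the Day 1 report did go out early?** Sections 13.1 and 13.2 list 4 + 5 = 9 endpoints. Set against 8.4 and Table 1:

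- Pre-wrap value at Visit 4: primary 2, 3 and 4 (range of motion, flexion-relaxation, pain on movement) and secondary 1 and 2 (NRS-Pain, ODI/RMDQ). That is 5.
- No pre-wrap value on Day 2, so Day 1 is the only comparator: secondary 3 (PGIC) and 4 (monitored activity). That is 2.
- No change measured: primary 1 (data collection) and secondary 5 (classifier correlation). That is 2.
- Total: 5 + 2 + 2 = 9.

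The questionnaire entries are less firm than the rest. In 8.4 the end-of-day questionnaires are PGIC and NRS only, so a post-wrap ODI/RMDQ rests on the general questionnaire row of Table 1 at Visit 5. That row is blank at Visit 3, where 8.4 places the Day 1 PGIC.

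**3. How much of a coaching shift would enter each contrast?** Let b be the level before coaching, d the coaching shift and s the share of it already present at Visit 4. Leave the wrap effect and other drift aside:

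- Visit 3 = b, Visit 4 = b + s·d, Visit 5 = b + d.
- Within Day 2: Visit 5 - Visit 4 = (b + d) - (b + s·d) = (1 - s)·d. This is 0 if the shift is fully present by Visit 4 (s = 1) and d if none of it is (s = 0).
- Between days: Visit 5 - Visit 3 = (b + d) - b = d, whatever s is.

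Section 11.2 plans one Wilcoxon test of movement for each day. The Day 1 test precedes any coaching. The Day 2 test is protected to the extent that the shift is already present at Visit 4. The repeated measures ANOVA on post-trial data has undefined time points. If it compares Visits 3 and 5, it would carry all of d. Section 11.2 names no test for PGIC or for change in activity.

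**4. What has to happen for d to differ from zero?** The report must be released between Visits 3 and 4. The clinician must reach the participant in that window, although no contact is scheduled. The coaching must then change Day 2 behaviour or ratings. The documents give no probability for any of these steps and no value for d or s.

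**The case for a change.** The strongest case for a change is that the time phrase is ambiguous, and release after each session is a natural reading of the sentence on its own. Two sites could act differently. Participants come from private physiotherapy clinics (8.1) and attend a clinic of their choice (8.3.1), so a treating clinician may be close at hand. The ANOVA in 11.2, and the correlations mapped across four time points, may span both days, so the exposure need not stop at PGIC and activity. A clarifying sentence would delay the report by about a day and leave visits, sample size and analysis alone.

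The ambiguity stands, and so does the point about the ANOVA. It would be too firm to say that 11.2 contains no between-day comparison. What does not stand is the step from an ambiguous phrase to a plan that needs repair. Giving Day 1 results to a participant before Day 2 would depart from both 8.2 and 8.4, so a site that follows the protocol does not do it. Release to a clinician who is not the investigator does not break the blind as 8.2 states it, and the documents do not say whether the two are the same person. Nor is a clarifying sentence free of risk. If it let the investigator see each participant's results once that participant had finished, it would create rolling unblinding that 8.2 does not provide for.

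**Conclusion.** No change to the plan is needed. Section 9.1 leaves it open whether release follows each session or both, but 8.2 and 8.4 already imply that Day 1 results do not reach the participant before Day 2 is complete. A release time would only write that down. With release after both sessions, 0 of 9 endpoints are affected. With early release and overnight coaching, 2 of 9 have no pre-wrap value on Day 2 to protect them, 5 of 9 have one, and movement is also open to the shift if the ANOVA compares Visits 3 and 5. The size of any shift cannot be estimated from the documents.

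This rests on two assumptions: that sites follow 8.2 and 8.4 as written, and that Figure 1 (the procedure summary, not available in the text read here) schedules no feedback between the days. If Figure 1 did show a report after Day 1, the conflict with 8.2 would be real and the conclusion would have to be revisited. In an uncontrolled feasibility study meant to inform a later randomised trial, what remains is a wording query.
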